Protocol: 03/21/16

CLINICAL PROTOCOL Lead Investigator: [name], PhD

Page 1 of 53

Compound: Axitinib; AG-013736

US IND Number: 112537 Protocol: UCI-10-55

Phase 2 Study of the Anti-Angiogenesis Agent Axitinib (AG-013736) in Patients with Stage III Malignant Melanoma

Protocol: 03/21/16

Page 2 of 53

Protocol Synopsis

Title:

Phase 2 Study of the Anti-Angiogenesis Agent Axitinib (AG-013736) in Patients with Stage III Malignant Melanoma

Rationale:

Stage III malignant melanoma is defined by lymph node involvement in a local basin (TNM staging: Any T; N1,2 or 3; M0) and has a 5 year survival rate of from 27 to 68%, indicating that is can often be an incurable and fatal disease for a significant proportion of patients. Surgical resection of the primary lesion and affected lymph nodes is the current standard of care. Although it would be of value to have an effective adjuvant therapy for this stage of disease, to date no treatment has led to significantly improved overall survival. While interferon has been applied with some benefit and can result in a significant prolongation in disease free survival, no overall survival benefit has been substantiated. IFN and its pegylated version are both approved by the FDA for this indication, but enthusiasm for their use is tempered by their significant toxicity. Like IFN, chemotherapy has not been demonstrated to prolong survival for stage III melanoma. New agents are required in order to improve the survival of patients with stage III melanoma. However, because large-scale clinical trials are often necessary to demonstrate the safety and effectiveness of a drug, it is desirable determine if new agents provide some measure of effectiveness of these new agents prior to investing in such studies. Because of the poor prognosis of patients with stage III melanoma and indications that anti-angiogenesis compounds might have clinically meaningful activity in this disease, a Phase 2 trial of the vascular endothelial growth factor receptor tyrosine kinase (VEGFR TK) inhibitor AG-013736 is warranted to determine its activity and tolerability for Stage III melanoma.

Indication:

Stage III melanoma

Objectives:

The primary objective of this study is:

• determine the response rate of axitinib in patients with Stage III melanoma as measured by the overall response rate by RECIST during the lead in phase. A response will also be considered to have occurred if there is a >/= 25% reduction in the involved nodal basin specific uptake value (SUV) on PET/CT (see Appendix C).

Secondary objectives with are to:

Protocol: 03/21/16

• determine progression-free survival (PFS)

- determine the safety profile of axitinib
- determine duration of response
- determine overall survival
- obtain blood samples for population pharmacokinetic analyses
- explore relationships between clinical response and plasma soluble proteins
- explore relationships between clinical response with tumor and host genomics

Number of Subjects/Sites:

Eighteen patients will be entered into the first stage of a 2-stage Simon Minimax design. If there is ≥ 1 response, 14 additional patients will be entered. For a total of up to 32 may be treated in order to gain additional safety and activity information should the initial 2-stage trial be positive at the end of Stage 2.

Study Country Location:

United States

Study Population:

In order to be eligible for this study, patients must meet all eligibility criteria and have no exclusion criteria. Major eligibility criteria include:

- Histologically documented stage III melanoma with measurable lymph node involvement.
- No more than prior systemic therapy for Stage III melanoma. (Prior adjuvant therapy with interferon for Stage II does not count as a prior therapy)
- At least 1 target lesion, as defined by RECIST, that has not been irradiated.
- Adequate bone marrow, hepatic, and renal function documented within 14 days prior to treatment.
- Age \geq 18 years.

Page 3 of 53

Page 4 of 53

Protocol: 03/21/16

- ECOG performance status of 0 or 1.
- Females must be either not of childbearing potential or of childbearing potential using adequate contraception or practicing abstinence.
- Written informed consent.

Patients must not have any exclusion criteria. Generally, the exclusion criteria are designed to assure patient compliance with the protocol, prevent enrolment of patients with conditions that might confound the evaluation of safety or efficacy, and increase safety by minimizing conditions that might pose a risk to patients treated with the test agent.

Study Design:

This Phase 2, open-label study of the investigational anti-angiogenesis agent axitinib, AG-013736. A 2-stage Simon Minimax design will be used with 18 treated patients in the first stage and 14 treated patients in the second stage. At least 1 patient must have a confirmed response (CR or PR) in the first stage in order to proceed to the second stage. At the end of the study, at least 4 confirmed responses in 32 treated patients must be observed in order to recommend further studies in this patient population.

For a total of up to 32 may be treated in order to gain additional safety and activity information should the trial be positive at the end of Stage 2.

Treatments:

Axitinib will be administered 5 mg orally twice each day (BID) continuously. Dose adjustments will be based on adverse events.

Protocol: 03/21/16

Endpoints:

Primary Endpoint(s):	Response rate according to RECIST criteria	
	A response will also be considered to have	
	occurred if there is a >/= 25% reduction in the	
	involved nodal basin specific uptake value (SUV)	
	on PET/CT (see Appendix C)	
Secondary Endpoints:	1) Progression-free survival (PFS)	
	2) Safety profile of AG-013736	
	3) Duration of response	
	4) Overall survival	

Page 5 of 53

Safety Measurement/Parameters:

Safety will be assessed by collecting adverse event information on each patient including results of physical examinations and laboratory testing.

Statistical Methods:

Demographic data will be displayed and summary statistics will be provided. The results of safety and efficacy evaluations will be tabulated and displayed.

The estimated response rate and its 95% confidence interval will be provided. The duration of response, progression-free survival, and survival will be summarized.

Study Schedule/Flowchart:

Study tests and procedures will include multiple examinations, laboratory tests, and radiographic procedures according to schedule of tests and procedures in the table below:

TABLE - SCHEDULE OF TESTS AND PROCEDURES

Protocol Activities	Screening	Study Treatme	ent					
	≤ 18 Days Prior to Enrollment	Day 1 to Day 56 (-3/+3)	Day 57 to Day 91 (-3/+3) Treatment Rest/ Pre-Op ^v	Surgery 14-21 Days Post Last Dose	Recovery 28 Days Post- Sugery ^w	Every 4 Weeks* Progression/Early Termination	Every 16 Weeks	Follow-up Day 28 After Last Dose ^x
Informed consent ^a	X							
Medical history ^b	X							
Concomitant treatment ^c	X	X				X		X
Physical exam ^d	X	X**	X		X	X		X
Weight, height, temperature ^e	X	X	X		X	X		X
Blood pressure, pulse ^f	X	X	X		X	X		X
Home blood pressure monitoring ^g		Pa	rticipant Ins	structed to M	lonitor thi	oughout st	udy.	
ECOG performance statush	X	X	X		X	X		X
Hematology ⁱ	X	X**	X		X	X		X
Chemistry ^j	X	X**	X		X	X		X
Urinalysis ^k	X	X**	X		X	X		X
12-Lead electrocardiogram ¹	X		X		X			
Fecal Immuchemical Test m	X							
Tumor measurements ⁿ PET/CT	X		X		X (post surgery baseline		X	
Soluble protein samples ^o Marker of drug activity		X	X			X ^y	X	
Tumor genomics ^p		X		X From node dissection				
Blood genomic sample ^q		X						
Safety assessment (adverse events) ^s		X	X		X			
Survival ^t		Throughout the study period						
Serum or urine pregnancy test ^u Until at least one year after the initial dose for the last treated patient	X	X			X		X	X
Axitinib Treatment		X				X		
Treatment held preoperatively			X					
Lymph node dissection				X				

Notes to Table

Tests and procedures should be done on schedule, but occasional changes by +/- 4 days are allowable for holidays, vacations, and other administrative reasons.

- * Cycle length is 4 weeks [two cycles prior to surgery].
- ** Unnecessary to repeat before first dose if screening assessment was performed within 7 days prior to first dose.
- ^a Any time prior to any procedures performed solely for this study.
- b Including use of nicotine products.
- ^c Should be collected from screening to the follow-up period.
- d After the initial complete examination, targeted examinations based on signs and symptoms may be performed.
- Height need not be collected after the first measurement.
- Blood pressure and pulse to be measured with the patient in the seated position after the patient has been sitting quietly for 5 minutes.
- Patients receiving AG-013736 will receive blood pressure monitoring devices. Patients should take blood pressure at least once each day and should be recorded in a patient diary.
- ^h See Appendix D for performance status scale.
- Hgb, Hct, WBC with differential, and platelets. Prothrombin time and partial thromboplastin time should be done prior to the first dose and then as clinically indicated.
- Blood urea nitrogen (BUN), creatinine, sodium (Na⁺), potassium (K⁺), chloride (Cl⁻), bicarbonate (HCO₃⁻) or CO₂, alkaline phosphatase, lactate dehydrogenase (LDH), alanine aminotransferase (ALT, or SGPT), aspartate aminotransferase (AST, or SGOT), total protein, albumin, total bilirubin, and glucose.
- Protein, glucose, and blood. If protein ≥2+ by semiquantitative method (eg, dipstick) then quantitate by 24-hour urine collection. Dose adjustment may be required. Screening urinalysis should include microscopic examination of the sediment.
- Additional ECGs as clinically indicated.
- ^m Subjects with a positive fecal immunochemical test (FIT) from blood test result should be evaluated for active gastrointestinal bleeding. Additional tests as clinically indicated.
- Tumors assessments by PET/CT will be performed every 8 weeks using RECIST criteria (see Appendix C). Response (CR/PR) requires confirmation at least 4 weeks after the response is noted. For patients who have not progressed after discontinuing study drug, additional tumor assessments should be performed approximately every 8 weeks until patient meets criteria for progression or alternate therapy started.
- ^o See Appendix F for collection, processing and shipping instructions. 10 ml of blood will be drawn for this sample.
- Optional for patients on Stage 1, required for patients entered on Stage 2 of the study. Second biopsy should be on Day 29 +/-4 days. A punch, core, or excisional biopsy should be used to obtain approximately 4 mm cube of tumor tissue. See Appendix G for processing and shipping instructions.
- Genomic analysis will be performed for each subject from a blood sample taken prior to dosing on Day 1. A 5 mL blood sample will be collected in a purple cap EDTA tube. Blood samples will be stored at -20°C until shipment on dry ice to the address given in the Study Manual. Appendix G has further details.
- Adverse events should be collected from the time of consent and throughout the study period until at least 28 days after the last dose of study drug and followed until resolution or stabilization.
- All patients should be followed for survival at least every 3 months after discontinuing study treatment until at least one year after the initial dose for the last treated patient.
- ^u Patient of childbearing potential must have a negative pregnancy test within 7 days prior to treatment and must be using appropriate birth control or practicing abstinence.
- ^v Minimum rest period is 14 days prior to surgery.
- Winimum rest period is 28 days post surgery; maximum rest period 56 days post surgery.
- Patients go off treatment after one year if they have not progressed.
- .y Done at first 4 week mark only.

TABLE OF CONTENTS

	PAGE
PROTOCOL SYNOPSIS	2

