3. METHODS

3.1. Study Design

This will be a 2-stage Minimax, Phase 2, open-label study of the investigational anti-angiogenesis agent AG-013736 in patients with locally metastatic stage III melanoma.

Patients will be consented at the time of diagnosis of stage III disease based on clinical or biopsy results. After obtaining a baseline PET/CT, patients will undergo 2 months of therapy with axitinib. Response will be determined by restaging PET/CT after two months of initial therapy. (Mohr P, Eggermont AM, Hauschild A, Buzaid A. Staging of cutaneous melanoma. Ann Oncol. 2009 20 Suppl 6:vi14-21.; Kumar R, Mavi A, Bural G, Alavi A. Fluorodeoxyglucose-PET in the

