6.1. Statistical Power and Sample Size Considerations

6.1.1. Sample Size

The primary purpose of this study is to determine the response rate in patients with advanced melanoma. This information would then be used to recommend further study of AG-013736 in this indication if favorable results occur. Implicit in this objective is the need to minimize the number of patients exposed to AG-013736 when unfavorable results occur.

These objectives are met through the use of a 2-stage Minimax design for Phase 2 protocols as discussed by Simon. The 2-stage design is used for testing hypotheses about the true response rate P. For each indication, we define p_0 , a response rate at which or below we consider AG-013736 to be ineffective or clinically unimportant, and p_1 , a minimum response rate that would merit further clinical development. The null hypothesis, H_0 , is $P \le p_0$. The alternate hypothesis, H_1 , is $P \ge p_1$.

The indication being studied in this protocol responds poorly to conventional chemotherapy. Therefore, p_0 and p_1 are set at low response rates of 5% and 20%, respectively. The α and β error rates are set at 0.10 and 0.10, respectively. These criteria result in a sample size for each stage of 18 and 14 patients (based on PASS 2002 software).

If enrolment to this study is stopped and AG-013736 is rejected at any stage because of lack of efficacy, the probability of falsely rejecting it is <0.10 when the true response rate is $\ge 20\%$. At the end of Stage 2, if AG-013736 is recommended for further study, the probability of failing to reject the agent is <0.10 when the true response rate is $\le 5\%$. If the true response probability is $\le 5\%$, there is approximately a 40% probability of terminating patient enrolment during Stage 1. However, if the true response probability is $\ge 20\%$, then there is only a 1.8% probability that a drug will be discarded erroneously in Stage 1.

Page 35 of 53

Protocol: 03/21/16

Up to 28 additional patients (for a total of up to 32) may be treated in order **to gain additional safety and activity information** should the trial be positive at the end of Stage 2. Their safety and efficacy data will be summarized with all other patients at the end of the study.

6.1.1.1. Stage 1

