APPENDIX C RECIST Criteria

At baseline, tumor lesions will be categorized as measurable or nonmeasurable (defined below).

All baseline evaluations should be performed as close as possible to the first day of study treatment and never more than 4 weeks before starting therapy.

Measurable Lesions

- Lesions that can be accurately measured in at least 1 dimension (longest diameter to be recorded) as \geq 2.0 cm with conventional techniques or \geq 1.0 cm with spiral CT scan.
- A tumor lesion that is situated in a previously irradiated area is eligible for measurable disease provided: 1) there has been documented disease progression in this site; 2) the criteria for measurability as outlined above are met; 3) this is not the only site of measurable disease.
- All measurements should be determined using a ruler, calipers or digital technology, and recorded on the CRF in metric notation.

Nonmeasurable Lesions

All other lesions, including small lesions (longest diameter <2.0 cm with conventional techniques or <1.0 cm with spiral CT) and truly nonmeasurable lesions. Truly nonmeasurable lesions include bone lesions, leptomeningeal disease, ascites, pleural or pericardial effusion, inflammatory breast disease, lymphangitis cutis or pulmonis, abdominal masses that are not confirmed and followed by imaging techniques, and cystic lesions.

Documentation of Target and Nontarget Lesions

All measurable lesions up to a maximum of 5 lesions per organ and 10 lesions in total, representative of all involved organs, should be identified as target lesions and measured and recorded at baseline. Target lesions (measurable) should be selected on the basis of their size (lesions with the longest diameter) and their suitability for accurate repetitive measurements (either by imaging techniques or clinically. A sum of the longest diameter (LD) for all target lesions will be calculated and reported as the baseline sum LD. The baseline sum LD will be used as reference by which to characterize the objective tumor response.

All other lesions (or sites of disease) should be identified as nontarget lesions and should also be recorded at baseline. Measurements are not required, and these lesions should be followed as present or absent.

Techniques for Assessing Measurable Disease

The same method of assessment and the same technique should be used to characterize each identified and reported lesion at screening and during follow-up. Imaging-based evaluation is

Protocol: 03/21/16

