APPENDIX G PROCESSING OF SAMPLES FOR GENOMICS ANALYSIS

Pharmacogenomic analysis of tumor samples:

After the patient grants informed consent for the biopsy, at least a 4 mm cube of tumor tissue from a superficial lesion should be obtained by a punch, core, or excisional biopsy. The first portion of the tissue will be placed in lactated Ringer's solution and refrigerated at 4°C for up to 3 days. The remainder of the 4 mm cube should be snap frozen in liquid nitrogen within one hour and stored at -70°C to -80°C. After the patient signs informed consent for peripheral blood sample collection, a blood sample (5 mL) will be collected in purple cap EDTA tubes and stored at -20°C. At the request of Pfizer, samples should be shipped to the analysis laboratory in dry ice according to shipping instructions provided by the gene laboratory identified in the Study Manual. The samples will be stored in a secure environment until the analysis has been completed.

The tumor and peripheral blood samples will be used to analyze expression of RNA as they may relate to clinical response (tumor regression and/or toxicity) to AG-013736. No other studies will be performed with these samples.

Tumor RNA will be extracted and prepared by standard protocols used by the laboratory. From total RNA, cDNA will be generated by reverse transcription. The cDNA will be then fluorescently labeled and hybridized on Affymetrix Gene chips (microarrays) according to instructions provided by the manufacturer. These microarrays contain oligonucleotides representing about 25,000 known genes that represent most of the genes present in the human genome.

Data from the chip analysis will be processed by gene chip expression software. The intensity of each probe set of the array will be captured and expression values calculated using a scanner. Data analysis will be analyzed to identify genes that are differentially expressed between the baseline and treated tumor samples. Data analysis will be performed to identify genes that are differentially expressed on tumors that have responded (or at least regressed) and those that remained stable or progressed. The set of genes that may be associated with the clinical response will be further confirmed by RT-PCR method.

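### An excisional research biopsy is permitted between the baseline and response scans, and no rule prevents removal of a target node from being scored as a response

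*Combined protocol and SAP*

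**What the plan says.** **Timing.** Section 3.5.8 puts the baseline lesion assessment within the 4 weeks before treatment. Section 3.1 says: "Response will be determined by restaging PET/CT after two months of initial therapy". The schedule places that scan in the Day 57 to Day 91 column. Note p reads: "Second biopsy should be on Day 29 +/-4 days. A punch, core, or excisional biopsy should be used to obtain" roughly a 4 mm cube of tumor. The same note makes the biopsy optional in Stage 1 and required in Stage 2.

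**Site.** Appendix G asks for "tumor tissue from a superficial lesion should be obtained by a punch, core, or excisional biopsy". Section 3.5.7 speaks of lymph node biopsies. Appendix C gives palpable lymph nodes, with skin nodules, as examples of superficial lesions that can be measurable.

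**Target lesions and scoring.** Appendix C makes targets of "All measurable lesions up to a maximum of 5 lesions per organ and 10 lesions in total", and adds that targets are chosen by size and by how well they can be measured repeatedly. Inclusion criterion 4 needs only one target. PR is a fall of at least 30% in the sum of longest diameters. CR is disappearance of all lesions. A sufficient fall in nodal-basin SUV also counts as a response. None of these definitions mentions a lesion that has been surgically removed.

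**Competing text.** The tumor genomics row of the schedule has a mark under Day 1 to 56 and a second one reading "X From node dissection". Section 1.3 takes the post-treatment material at lymph node resection, and Section 3.5.7 places that resection after neoadjuvant therapy ends. Section 6.2.7.1 says tumor samples are obtained when possible, which does not match a required biopsy.

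**The concern.** The primary endpoint is a within-patient change between two scans. A procedure that may remove measured tissue between those scans can produce a qualifying change with no drug effect. The decision rules are sensitive to this: one response in 18 opens Stage 2, and four in 32 lead to a recommendation for further study. A single patient scored as a responder because a node was taken out could change the outcome.

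The remaining safeguards do not cover the case. Section 6.2.2 discards data only after additional therapy that follows discontinuation. Section 6.2.1 makes the independent assessment primary, but nothing requires that the reader be told a node was excised. Section 3.5.8 says no confirmatory scan will be done. One would not help in any case, because an excised node stays absent.

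**Working it through.** **Inputs, all from Section 6.1.1 and its subsections.** Null rate 0.05, alternative rate 0.20, α = β = 0.10. For the stage sizes: "These criteria result in a sample size for each stage of 18 and 14 patients". Continue with at least 1 response in 18; succeed with at least 4 in 32.

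**1. Reproducing the design.** Let X be the number of Stage 1 responders, binomial with n = 18.
- Early stopping: 0.95^18 = 0.397 at a 5% rate and 0.80^18 = 0.018 at 20%. These match the protocol's 40% and 1.8%.
- P(pass) = sum over x ≥ 1 of P(X = x) × P(at least 4 − x responders among the 14 Stage 2 patients).
- At 5%: 0.3763×0.0301 + 0.1683×0.1530 + 0.0473×0.5123 + 0.0109×1 = 0.072.
- At 20% the same formula gives 0.901. The design holds as stated.

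**2. Order of events.** Baseline scan (before Day 1), biopsy (29 ± 4, so Day 25 to 33), response scan (Day 57 or later). Under note p the biopsy lies between the two scans.

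**3. Effect of excision on the sum of diameters.** With k equal-sized targets, one removed and no drug effect, the fall is 1/k.

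| Targets | Fall | Meets the 30% PR rule? |
|---|---|---|
| 1 | 100% | Yes; CR if no other lesion remains |
| 2 | 50% | Yes |
| 3 | 33% | Yes |
| 4 | 25% | No |

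Unequal sizes can go either way. Removing the 1.0 cm node from a 2.0 + 1.0 cm pair gives 1.0/3.0 = 33%, a PR. Removing it from a 3.0 + 1.0 cm pair gives 1.0/4.0 = 25%, not a PR.

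**4. Effect on the decision rule.** Fix m of the 14 Stage 2 patients as false responders and keep everyone else at 5%. The second factor in step 1 becomes P(at least 4 − m − x responders among 14 − m). For m = 1:

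0.3763×0.1354 + 0.1683×0.4867 + 0.0473×1 + 0.0109×1 = 0.0510 + 0.0819 + 0.0473 + 0.0109 = 0.191.

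| False responders in Stage 2 (assumed) | P(pass) at a true 5% rate |
|---|---|
| 0 | 0.072 |
| 1 | 0.191 |
| 2 | 0.399 |
| 3 | 0.603 |

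One false responder in Stage 1 meets the continue rule alone. With the other 17 Stage 1 patients at 5%, P(pass) is 0.201.

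**5. As a proportion.** If a share f of Stage 2 patients becomes false responders through excision, their response rate is 0.05 + 0.95f. P(pass) is then 0.108 at f = 2%, 0.171 at 5% and 0.283 at 10%. The documents give no value for f.

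**The case against.** The strongest reply has four parts.

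- **Little tissue is needed.** About 4 mm is wanted, and punch and core are listed beside excision. A punch or core sample of a target of 1 cm or more would usually not reach 30%. This stands: no text directs removal of a whole node.
- **Target selection by suitability for repeat measurement.** A node due to be excised is a poor candidate under Appendix C. That is relevant, but it is not a bar. It sits beside the instruction to take all measurable lesions up to the cap, and nothing requires the biopsy site to be known when targets are chosen.
- **The Day 29 timing rests on one note.** The schedule row and Section 1.3 point to the dissection specimen. The mark in the Day 1 to 56 column does not settle it, because the blood genomic sample, drawn before dosing on Day 1, is marked in the same column. This stands, and if the conflict is resolved towards dissection the problem disappears.
- **The error rates assume the cases.** This also stands. The number could be zero.

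A reader might go further and infer that the biopsied node is nearly always a target, or that a site following the plan would record a false response. The documents do not support either. Appendix G's superficial lesion may be a skin nodule, and Section 1.1 includes nearby skin and lymphatic spread in stage III. Lesions under 1.0 cm on spiral CT are nonmeasurable. No frequency is given for excision or for sampling of targets. Nor does the requirement in Stage 2 imply excision there; it requires a biopsy, by any of the three techniques.

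**Conclusion.** The concern holds as a gap in the rules for the primary endpoint, conditional on note p being operative. The plan permits excision of a target node between the two scans and does not say how the result is scored, so removal can count as PR or CR. One such patient in Stage 2 takes the false-positive probability from 0.072 to 0.191, above the stated alpha of 0.10.

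This rests on three assumptions: the Day 29 biopsy is actually taken, at least one site excises a target, and the excised node makes up enough of the sum (or of the basin SUV) to cross the threshold. The figures for two or three false responders show sensitivity and are not forecasts.

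Whether the gene-expression comparison mixes on-drug tissue (Day 29) with off-drug tissue (dissection) is a separate exploratory matter and does not touch the primary endpoint.

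**What to change.** 1. Reconcile note p with the schedule row and Sections 1.3 and 3.5.7 on whether a Day 29 biopsy is taken. If the dissection specimen is the treated sample, delete the Day 29 sentence and nothing further is needed.
2. If a biopsy between the scans is kept, state in note p and Appendix C that:
   - a target lesion may be sampled by punch or core only, and remains a target;
   - excision before the response scan is limited to a lesion named as nontarget before baseline;
   - a lesion wholly or partly excised between the scans cannot contribute to CR or PR: it is left out of the sum of diameters and the SUV comparison at both scans, and its absence does not count as disappearance;
   - a patient left with no target lesion is counted as a non-responder.
3. Record the biopsied lesion and the technique on the CRF, and pass this to the independent reader.

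Keeping a punched or cored lesion as a target matters. If every sampled lesion became nontarget, a patient whose only target was cored would have nothing to score. The separate line on disappearance is needed because CR also requires nontarget lesions to disappear.

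The cost is protocol wording and a CRF field, with no added procedure. A few patients may have one fewer target lesion or be scored as non-responders, which errs towards a lower response rate.
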